4.3 PREMATURE DISCONTINUATION OF STUDY THERAPY

Study treatment, defined as the dosing and administration of study medication according to study specification, will be discontinued for an individual participant if any of the following occurs:

- A toxicity management discontinuation criterion is met for brentuximab vedotin (Section 5.2).
- The participant's dose of methotrexate, mycophenolate mofetil, azathioprine, or prednisone exceeds the allowed dose (Section 5.3.1.1 and section 5.3.3).
- The investigator or the National Institute of Allergy and Infectious Diseases
 (NIAID) medical monitor determines that it is in the participant's best interest to
 discontinue treatment for any reason, including non-adherence to the protocol.
- The participant requests that treatment be halted.
- The participant becomes pregnant (see section 8.8 Reporting Pregnancy).

Further care will be provided according to the judgment and practice of the principal investigator.

At this time the participant will complete all assessments listed for the discontinuation visit (DSC). The participant will be asked to return for safety follow-up visits at weeks 12, 24, 36, and 48, if these visits have not already occurred.

If study treatment is discontinued, the NIAID Medical Monitor should be notified.

4.4 PREMATURE TERMINATION OF A PARTICIPANT FROM THE STUDY

Withdrawal of consent. Participants who withdraw consent will be asked to complete an end-of-study visit to include the assessments listed in visit 11.

Failure to return. Participants who do not return for visits and who do not respond to repeated attempts by the site staff to have them return will be considered lost to follow-up.

Investigator decision. The investigator or the National Institute of Allergy and Infectious Diseases (NIAID) medical monitor determines that participation in the study is no longer in the best interest of the participant.

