8.4 COLLECTING AND RECORDING ADVERSE EVENTS

8.4.1 Collection Period

All adverse events, regardless of NCI-CTCAE severity grade should be recorded in the study source documentation per the criteria below:

- Adverse events will be collected from the time the subjects signs the informed
 consent until he/she initiates study intervention or until he/she is determined to be
 ineligible to receive study intervention, if the investigator determines that the
 adverse event is related to a study-mandated procedure, treatment, or change in
 treatment.
- For all participants, adverse events will be collected from the time of initiation of study intervention until he/she completes study participation or until 30 days after he/she prematurely withdraws (without withdrawing consent) or is withdrawn from the study.

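### Section 4.4 allows a consenting participant to be removed on a best-interest judgement with no follow-up attached, so part of the week-48 primary safety window can go unobserved

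*Protocol*

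**What the plan says.** **Stopping drug (Protocol 4.3).** Treatment stops if a toxicity criterion in 5.2 is met, or if the investigator or NIAID medical monitor judges that stopping treatment is best for the participant, among other reasons. The participant then has a discontinuation visit and is "asked to return for safety follow-up visits at weeks 12, 24, 36, and 48", where those visits are still to come.

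**Ending participation (Protocol 4.4).** The same two parties may end participation if either "determines that participation in the study is no longer in the best interest of the participant". The section gives no criterion that separates this from the 4.3 decision, and no visit or follow-up goes with it. The only exit visit in 4.4 is for another group: "Participants who withdraw consent will be asked to complete an end-of-study visit to include the assessments listed in visit 11".

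**Adverse event collection (Protocol 8.4.1).** After the start of study intervention, collection runs to completion of participation or "until 30 days after he/she prematurely withdraws (without withdrawing consent) or is withdrawn from the study". Section 8.4.3 sets a similar 30-day limit for following adverse events already recorded; serious events are covered separately there.

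**Endpoint and analysis.** The primary endpoint is at least one Grade 3 or higher adverse event at or before week 48 (3.4.1). It is analyzed in everyone who received any study drug or placebo, and also in the PP48 sample (9.1.1, 9.2.1). Missing data are not imputed (9.2.4). Each cohort has 6 active and 2 placebo participants (9.3).

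**The concern.** Two best-interest decisions by the same people lead to opposite follow-up, and the protocol does not say how to choose between them. If 4.4 is used, a participant who has not withdrawn consent and can still be reached leaves safety observation 30 days later by a staff decision.

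The trial exists to measure safety over 48 weeks. An adverse event that was never collected cannot be recovered in analysis, and a cohort with 6 active participants has little room to lose one. After a first full dose, section 4.5 replaces only early discontinuations unrelated to treatment or disease, so a participant removed for tolerability or worsening disease would not be replaced. The PP48 definition counts infusions and major deviations, not completed follow-up, so it does not clearly exclude someone removed after the last infusion.

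Monitoring could be touched as well. The week-24 safety review could lack complete data on anyone removed before about week 19.7 (24 − 30/7). Stopping rule 5 in 8.11.3 needs Grade 3 or higher neuropathy in two different participants, so one unseen event could keep it from being triggered.

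**Working it through.** **1. The plan's own figures.** Table 2 follows from 1 − (1 − p)^n. For n = 6 and p = 0.1, 0.2, 0.3 this gives 0.469, 0.738, 0.882 (stated: 0.47, 0.74, 0.88). For n = 3 it gives 0.271, 0.488, 0.657 (stated: 0.27, 0.49, 0.66). All seven Clopper-Pearson rows of Table 3 also reproduce, including 0/6 with upper limit 0.459 and 1/6 with limits 0.004 and 0.641. These tables are not in dispute.

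**2. Who is exposed.**

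| Situation | Route | Primary endpoint |
|---|---|---|
| Meets a 5.2 toxicity criterion | 4.3; the end of 5.2.4 also points there | Safety visits to week 48 kept |
| Removed after a Grade 3 or higher event | 4.4 | Event already counted |
| Removed under 4.4 with no Grade 3 or higher event, consent not withdrawn | 4.4, then 8.4.1 | Unobserved from 30 days after removal |

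Only the last row is a problem. Lower-grade toxicity or worsening disease are examples of how it could arise.

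**3. How much of the window is lost.** Collection ends at removal week + 30/7, and 30/7 = 4.29 weeks. The whole window is covered only if removal comes at or after 48 − 4.29 = week 43.7.

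| Removal week (assumed) | Collection ends | Share of 48 weeks unobserved |
|---|---|---|
| 12 | 16.3 | (48 − 16.3)/48 = 66% |
| 21 | 25.3 | (48 − 25.3)/48 = 47% |

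**4. Effect of one participant on a cohort's active-arm result.** The upper limit for zero events in n is 1 − 0.025^(1/n).

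| Case | Result | Upper 95% limit | P(at least 1 event) at p = 0.1 / 0.2 / 0.3 |
|---|---|---|---|
| Event seen | 1/6 | 0.641 | 0.47 / 0.74 / 0.88 (n = 6) |
| Event unseen, participant kept as a non-event | 0/6 | 0.459 | – |
| Event unseen, participant excluded | 0/5 | 0.522 | 0.41 / 0.67 / 0.83 (n = 5) |
| Two participants excluded, none of the rest with an event | 0/4 | 0.602 | 0.34 / 0.59 / 0.76 (n = 4) |

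The last column is the chance of seeing any event with that many fully observed participants.

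**5. Illustration only: chance of a later unseen event after removal at week 12.** Assume a constant hazard and a true 48-week risk p of 20%, 40% or 60%; none of these comes from the protocol.

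- Event-free to the end of collection (week 16.3): 1 − (1 − p)^0.66 = 14%, 29%, 45%.
- Event-free at week 12: (1 − p)^(4.29/48) − (1 − p)^(36/48) = 13%, 27%, 42%.

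Dosing ends at week 21, and a removed participant is already off drug, so a constant hazard may well overstate the later risk.

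**The case against.** **Toxicity goes elsewhere.** A reader might infer that participants stopped for toxicity lose follow-up. The text does not support that. A 5.2 criterion leads to 4.3, the end of 5.2.4 repeats this, and other events judged significant lead first to suspension of dosing. Loss needs a separate decision under 4.4. This part of the objection stands and narrows the point.

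**Section 4.5 may already cover it.** Its last sentence applies the 4.3 procedures to anyone given any part of an infusion. Read alone, that covers the whole safety sample. But it sits in the replacement rule and says nothing about 4.4 or the 30-day limit in 8.4.1, so it does not clearly override either. It adds to what needs reconciling.

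**The two decisions differ in object.** One concerns treatment and the other participation, so there is no strict contradiction. That is fair. The gap is that no criterion tells a site which applies, while the consequences for the primary endpoint are very different.

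**Informative loss is not shown.** It is tempting to say that such removals will come mostly from toxicity or worsening, and mainly in the higher-dose arms. The protocol gives no such breakdown, trial personnel other than the site pharmacist are blinded, and disease can worsen on placebo. Informative loss is possible, not established.

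**The neuropathy timing does not transfer.** The medians of about 34 and 38 weeks to Grade 3 neuropathy in 1.4.1.1 come from lymphoma trials, one with up to 16 doses and one with a median treatment of about 48 weeks. Here the maximum is eight doses. In the older lymphoma population of 1.4.1.1.1 the medians were 15.4 and 16.6 weeks. None of these sizes the loss in this trial.

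**Conclusion.** The point holds in a limited form. The protocol allows a consenting, reachable participant with no Grade 3 or higher event to be taken out of safety observation on a best-interest judgement, with no exit visit required and collection ending 30 days later. Removal before about week 43.7 leaves part of the primary endpoint window unobserved. One unseen event changes a cohort's active-arm result from 1/6 to 0/6 and its upper limit from 0.641 to 0.459, or to 0.522 if the participant is excluded.

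The expected loss cannot be sized, because the protocol gives no removal rate. The removal weeks and the constant-hazard figures are assumptions. How a partly observed participant enters the proportion may be settled in the statistical analysis plan and is not part of this point. The case for change rests on an avoidable, unrecoverable loss in very small groups, set against a low cost.

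**What to change.** At the next amendment, reconcile 4.4 and 8.4.1 with 4.3:

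- Keep the power to end participation, but state how that decision differs from the best-interest stop of drug in 4.3.
- Provide that a treated participant removed by investigator or monitor decision, who has not withdrawn consent and can be reached, continues adverse event and serious adverse event collection to week 48. This can use the 4.3 safety visits, or remote contact where no in-person neuropathy assessment is needed. Visit 9 is already remote on that footing: Appendix 1 makes an exception for participants being followed for a neuropathy event.
- Adjust the 30-day limit in 8.4.1, and the matching limit in 8.4.3, so that neither cuts this follow-up short.
- Ask everyone who leaves early, not only those who withdraw consent, for the visit 11 assessments.

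The cost is a short text change and a few extra safety contacts, on a visit schedule that already exists for participants who stop drug.

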4.5 REPLACEMENT OF STUDY PARTICIPANTS

Participants will be replaced if they do not receive 1 full dose of study medication, or if they discontinue before receiving 6 of 8 doses for a reason unrelated to treatment or the disease. A maximum of 8 extra participants may be enrolled in a single dosing cohort under these criteria. The procedures in section 4.3 will be followed for participants who receive any part of an infusion of study medication.

Protocol ITN075AI: BRAVOS Brentuximab Vedotin for Systemic Sclerosis

5. STUDY THERAPIES, MEDICATIONS AND PROCEDURES

5.1 INVESTIGATIONAL MEDICATION: BRENTUXIMAB VEDOTIN

5.1.1 Formulation and Packaging

Brentuximab vedotin 50 mg is supplied as a sterile, white to off-white lyophilized, preservative-free cake or powder in a single-use vial for reconstitution. The pH of reconstituted product is approximately 6.6. Brentuximab vedotin will be provided by the manufacturer. Brentuximab vedotin will be distributed to sites by a designated drug distributor under contract to NIAID.

5.1.2 Placebo Preparation

Brentuximab vedotin placebo consisting of 0.9% Normal Saline will be prepared by the site pharmacist.

5.1.3 Dosage, Handling, Preparation, and Administration

5.1.3.1 Dosage

Brentuximab vedotin dose will be determined based on the participant's weight. Rounding is permissible within 5% of the nominal dose. Weight from the previous visit may be used to calculate the brentuximab vedotin dose unless the weight was obtained more than 30 days previously. Actual weight will be used except for participants weighing greater than 100kg; the dose for participants with weight greater than 100 kg will be calculated based on 100 kg.

Brentuximab vedotin or placebo will be administered every 3 weeks from study week 0 through study week 21, according to the schedule described in Section 3.1:

- Cohort 1 will receive 0.6 mg/kg brentuximab vedotin or placebo (to a maximum dose 60 mg).
- Cohort 2 will receive 1.2 mg/kg brentuximab vedotin or placebo (to a maximum dose 120 mg).
- Cohort 3 will receive 1.8 mg/kg brentuximab vedotin or placebo (to a maximum dose 180 mg).

5.1.3.2 Storage Conditions and Handling Precautions

Brentuximab vedotin is an anti-neoplastic product, and must be handled and disposed according to guidelines provided by Occupational Safety and Health Administration (OSHA) for hazardous drugs [78]. Handling precautions include masks, protective clothing, gloves, and vertical laminar airflow safety cabinets.

Brentuximab vedotin vials must be stored at 2-8°C and protected from light in the original container prior to reconstitution.

Protocol ITN075AI: BRAVOS Brentuximab Vedotin for Systemic Sclerosis Following reconstitution and dilution, brentuximab vedotin solution can be stored at 2-8° C and administered within 24 hours of reconstitution and dilution.

Do not freeze.

5.1.3.3 Preparation

5.1.3.3.1 Reconstitution

Brentuximab vedotin will be reconstituted according to the prescribing information [55]. The number of 50 mg vials of brentuximab vedotin needed will be calculated based on the participant's weight, as described in section 5.1.3.1. Each vial will be reconstituted with 10.5mL of Sterile Water for Injection USP, to yield a single-use solution containing 5mg/ml brentuximab vedotin.

The stream of Sterile Water will be directed toward the wall of the vial and not directly at the cake or powder. Gently swirl the vial to aid dissolution. Do not shake. Upon inspection, the reconstituted solution should be clear to slightly opalescent, colorless, and free of particulate matter.

Reconstituted brentuximab vedotin will be immediately diluted into an infusion bag. If not diluted immediately, reconstituted brentuximab vedotin will be stored according to section 5.1.3.2.

The unused portion of brentuximab vedotin vials will be discarded according to guidelines provided by OSHA for hazardous drugs [78].

5.1.3.3.2 Dilution

Reconstituted brentuximab vedotin will be diluted according to the prescribing information [55]. The required volume of 5 mg/mL brentuximab vedotin will be calculated based on the participant's weight. This volume will be withdrawn from the vials and immediately added to an infusion bag containing a minimum volume of 0.9% Normal Saline Injection, 5% Dextrose Injection, or Lactated Ringer's Injection. The infusion bag will be gently inverted to mix.

Following dilution, brentuximab vedotin will be infused immediately according to the instruction in section 5.1.3.4. If not infused immediately, brentuximab vedotin will be stored according to section 5.1.3.2.

5.1.3.4 Administration and Monitoring

5.1.3.4.1 Pre-medication

Routine premedication for brentuximab vedotin is not indicated [55]. However, premedication should be administered to any participant who experienced a Grade ≤ 2 infusion reaction during or following a previous brentuximab vedotin administration. These participants should receive premedication one hour (plus or minus approximately 15 minutes) prior to the brentuximab vedotin infusion with oral acetaminophen 650 mg, oral diphenhydramine 50 mg or equivalent antihistamine, and intravenous methylprednisolone 20 mg or equivalent corticosteroid.

Version 5.0

5.1.3.4.2 Monitoring

Brentuximab vedotin infusions will occur in a setting with access to ACLS certified personnel, resuscitative drugs, monitoring devices, and CPR equipment. Vital signs must be assessed prior to the infusion, approximately every 15 minutes during the infusion, at the end of the infusion, and 1 hour after the completion of the infusion. After the infusion is complete, the intravenous line must remain in the participant for at least 1 hour to facilitate administration of medical management if needed.

5.1.3.4.3 Administration

Brentuximab vedotin or placebo will be administered as an intravenous infusion over approximately, but no less than, 30 minutes, as described in the prescribing information at study weeks 0 through 21. Hematology and serum chemistry results must be obtained within 72 hours prior to infusions at study weeks 3 through 21.

Brentuximab vedotin must not be administered as an intravenous (IV) push or bolus. Do not mix brentuximab vedotin, or administer as an infusion, with any other medicinal products. If an infusion related reaction occurs, the infusion should be interrupted and medical management instituted as needed (e.g., corticosteroids, epinephrine, bronchodilators, or oxygen). In cases of mild reactions (\leq Grade 2), the infusion can be resumed at a 50% rate reduction when symptoms have resolved and are no longer deemed a threat to the participant's well-being. If anaphylaxis occurs, immediately and permanently discontinue brentuximab vedotin and administer emergency medical therapy.

5.2 TOXICITY MANAGEMENT OF BRENTUXIMAB VEDOTIN

5.2.1 SARS-CoV-2 Infection or Exposure

Suspend brentuximab vedotin or placebo administration if the participant develops symptomatic or asymptomatic SARS-CoV-2 infection:

- Participants with mild or moderate SARS-CoV-2 infection should be evaluated for treatment with a monoclonal antibody product authorized by the FDA for the treatment of COVID-19, as soon as possible following confirmation of the infection and within 10 days of symptom onset [69-71]. Use of other FDA authorized or approved therapeutic agents should also be considered as they become available, depending on the clinical circumstance.
- Brentuximab vedotin may be restarted at the next scheduled dose, if symptoms have been absent for at least 10 days, or in the case of asymptomatic infection at least 10 days have passed since the positive SARS-CoV-2 test. In addition, a negative PCR test for SARS-CoV-2 must be obtained prior to restarting brentuximab vedotin or placebo administration.
- Any participant who has close contact with a SARS-CoV-2 infected individual should be evaluated for post-exposure prophylaxis as soon as possible after exposure [69, 70].

Version 5.0

5.2.2 Other Infection or AE

Suspend brentuximab vedotin or placebo administration if the participant develops any other infection or AE that the investigator judges to be significant. If the infection or AE resolves, brentuximab vedotin may be restarted at the next scheduled dose.

5.2.3 Peripheral Neuropathy

Suspend brentuximab vedotin administration if the participant develops a Grade 2 peripheral neuropathy. If the peripheral neuropathy resolves, brentuximab vedotin may be restarted at a lower dose as follows: the affected participant in Cohort 1 will restart brentuximab vedotin at 0.3 mg/kg/dose, in Cohort 2 will restart brentuximab vedotin at 0.6 mg/kg/dose, and in Cohort 3 will restart brentuximab vedotin at 1.2 mg/kg/dose.

5.2.4 Permanent Discontinuation of Study Medication for Toxicity

Permanently discontinue brentuximab vedotin if any of the following occurs:

- The participant misses > 3 doses of brentuximab vedotin.
- Grade 2 peripheral neuropathy recurs after brentuximab vedotin suspension and dose modification, as described above.
- Grade 3 or greater peripheral neuropathy.
- Grade 3 or greater neutropenia or thrombocytopenia.
- Grade 3 or greater infusion reaction.
- Anaphylaxis, defined as a serious allergic reaction that is rapid in onset and may cause death (see Appendix 2) [79].
- New onset rash consistent with Stevens-Johnson syndrome, toxic epidermal necrolysis, or other drug reaction.
- eGFR $< 30 \text{ ml/min}/1.73 \text{ m}^2$.
- Potential drug-induced liver injury, defined as all three of the following:
 - o ALT or AST elevation > 3 times upper limit of normal (ULN), and
 - Total bilirubin > 2 times ULN, without initial findings of cholestasis (elevated serum alkaline phosphatase), and
 - No other immediately apparent possible causes of ALT or AST elevation and hyperbilirubinemia, including but not limited to viral hepatitis, preexisting chronic or acute liver disease, or the administration of other drugs known to be hepatotoxic.
- Two or more Grade 3 or greater infections, or one Grade 4 infection.

• A suspected case of PML.

A diagnosis of PML should be considered in any participant presenting with new-onset or deteriorating neurological signs and symptoms. The participant should be referred to a neurologist or other appropriate specialist for evaluation. If PML is suspected, this should be immediately reported to the NIAID Medical Monitor. The appropriateness of continuing study medication, while the case is being assessed, should be discussed.

If brentuximab vedotin is discontinued, the procedures in Section 4.3 should be followed.

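### Section 5.2.4 requires a permanent stop for suspected PML, then leaves continued dosing during assessment open to discussion

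*Protocol*

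**What the plan says.** Section 5.2.4 opens its list with "Permanently discontinue brentuximab vedotin if any of the following occurs", and the last item is "A suspected case of PML". Suspicion alone is the trigger; confirmation is not required. Section 4.3 has no PML rule of its own. It says that study treatment "will be discontinued for an individual participant if any of the following occurs", and its first item is the meeting of a toxicity discontinuation criterion under Section 5.2.

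The paragraph below the list in Section 5.2.4 sets out a pathway. It begins "A diagnosis of PML should be considered in any participant presenting with new-onset or deteriorating neurological signs and symptoms" and asks for referral to a neurologist or other specialist. It goes on "If PML is suspected, this should be immediately reported to the NIAID Medical Monitor", and the next sentence is "The appropriateness of continuing study medication, while the case is being assessed, should be discussed".

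**The concern.** The list item leaves no decision about dosing: once PML is suspected, study drug stops for good. The paragraph treats that same decision as open while the case is worked up. Two sites could act differently on the same presentation, and whichever acts would depart from one of the two instructions. PML is the risk for which the product carries a black box warning (Section 1.4.1), so this is the event for which the dosing rule should be least open to interpretation. At stake is whether a participant under evaluation for PML could receive a further infusion after a discussion that the list item rules out.

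**Working it through.** The protocol states no figure on this point, so the check is a comparison of text, followed by schedule arithmetic.

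**1. The two instructions side by side**

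| | List item, Section 5.2.4 (with Section 4.3) | Paragraph below the list, Section 5.2.4 |
|---|---|---|
| Condition | PML suspected | PML suspected |
| Dosing consequence | Permanent stop, mandatory | Whether to continue is to be discussed |
| Confirmation needed | No | Applies while assessment is under way |

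The conditions match. The paragraph does start from a wider group, in whom PML is only to be considered. But the sentence on continuing follows directly on the one that starts from suspicion, and it refers to the case being assessed. The natural reading is that it concerns suspected PML, which is the state named in the list.

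**2. Does another section settle which prevails?**

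- Section 5.2.2 calls for suspension for any other infection or adverse event that the investigator judges significant, with restart possible after resolution. It could support a hold, but only on the investigator's judgment, and its restart provision also differs from a permanent stop.
- Section 4.3 separately lets the investigator or the NIAID medical monitor stop treatment in the participant's best interest. This is a power, not a rule for suspected PML.
- Section 8.5.2 makes suspected PML reportable within 1 business day. It does not address dosing.
- Section 8.11.1 provides for DSMB review of an event that could contribute to a stopping rule. It does not address the participant's next dose.
- Section 8.11.3 names one case of PML as a trigger for DSMB review. It implies that a participant under that review does not continue dosing during an enrollment halt. It speaks of a case, not of a suspicion under assessment.

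None of these gives either instruction precedence.

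**3. When can the conflict operate?**

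Inputs: infusions every 3 weeks at weeks 0, 3, 6, 9, 12, 15, 18 and 21, eight in all (Sections 3.1 and 5.1.3.1); 48 weeks of participation (Section 3.3).

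- Share of participation in which infusions remain: 21/48 = 0.4375, about 44%.
- Infusions remaining after infusion k: 8 − k. This gives 7 after the first, 4 after the fourth and 0 after the eighth.

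The list item allows none of the remaining infusions. The paragraph leaves open those that fall due during assessment. The protocol gives no duration for the work-up. On the nominal schedule, an assessment of 21 days or more spans at least one due date while infusions remain; a shorter one may or may not.

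**The case against.** The strongest reply is that the two texts can be followed together. The list item and Section 4.3 are imperative, while the sentence only asks for a discussion. A site can stop on suspicion, report at once, and discuss. That discussion includes the Medical Monitor, who has authority to stop treatment, and the DSMB may be brought in. It can also be said that suspicion is not defined, and that neuropathy is common with this drug (Section 1.4.1.1 cites 55% in the trial database and 62% on monotherapy). A discussion step while neurological signs are evaluated is therefore understandable.

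Much of this stands. A reader might infer that the protocol permits dosing during a PML work-up. The text does not support that: the sentence authorises no dose, and a site that applies the stricter rule gives none. The safeguards make an unreviewed infusion unlikely.

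What does not stand is that nothing is left to correct. If the permanent stop has already taken effect, the appropriateness of continuing is no longer a question. Asking it reopens an option that the list item has closed. The safeguards rest on discretion or review and do not supply the missing order of precedence.

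**Conclusion.** The conflict is real and should be corrected, but its practical reach is small. It concerns individual patient safety for a rare event, can arise only while infusions remain, and changes no estimate, endpoint analysis or sample size figure. The conclusion rests on reading the sentence with the one before it, which starts from suspicion.

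A reader might try to size the problem from the PML incidence below 0.05% quoted in Section 1.4.1.2. With 3 × 6 = 18 planned active participants, the chance of any case at that bound is 1 − (1 − 0.0005)^18 = 0.00896, just under 0.9%. This does not measure the issue: it is a rate of PML in cancer patients, whereas the rule turns on suspicion in this population during treatment. The protocol gives no rate of suspected PML, so 0.9% is neither an estimate nor a bound. The chance that an infusion would be given cannot be derived from the document.

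**What to change.** In Section 5.2.4, delete the sentence on discussing continuation and put in its place: *Study medication must be permanently discontinued once PML is suspected; no further infusion will be given.* This is one sentence in an amendment. A participant later cleared of PML still loses the remaining 8 − k infusions, but the list item already requires that, so nothing is added.

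If the sponsor prefers to allow resumption, take suspected PML out of the permanent list and state one rule: *Suspend dosing when PML is suspected. Discontinue permanently unless PML is excluded by the specialist evaluation and the NIAID Medical Monitor agrees.* The existing criterion, "The participant misses > 3 doses of brentuximab vedotin", would still apply. The costs of this option are:

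- A participant who resumes has missed at most 3 infusions.
- With no earlier misses, the fourth missed infusion falls due 4 × 3 = 12 weeks after the last one given, which is possible only if k ≤ 4. A participant not cleared before then loses all remaining infusions, up to 8 − 1 = 7.
- Two missed infusions leave 8 − 2 = 6, below the 7 of 8 that Section 9.1.1 requires for PP24, PP36 and PP48. Two or more misses therefore remove the participant from those samples, including the PP48 sample used for the primary endpoint. The safety sample is unaffected.

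Section 4.3 follows by reference and needs no edit under either option. Sample size, endpoints and planned analyses stay as they are.
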